## **11.1 Adverse Events**

### **11.1.1 Reportable AEs**

11.1.1.1 All AEs that occur after the informed consent is signed and baseline assessments are completed (including run-in) through the day preceding the day of surgery must be recorded on the AE CRF (paper and/or electronic) whether or not related to study agent.

11.1.1.2 AEs not related to surgery that occur from the day of surgery through Study visit 2 (up to 21 days post surgery) must be recorded on the AE CRF (paper and/or electronic) whether or not related to study agent.

11.1.1.3 All SAEs, including all hospitalizations, during the study period will be reported as per DCP SAE reporting procedures, with the following exception:

Hospitalization for planned surgery will not be reported. However, if this hospitalization event lasts longer than the usual period at the institution (as determined by the Site Principal Investigator), it will be reportable as an SAE. Adverse events (AEs) relevant to the prolongation of this hospitalization will be collected and reported on AE CRFs.

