#### Role of tamoxifen therapy for women with DCIS

Tamoxifen (TAM) has been proven to reduce risk of both local recurrence and new primary breast cancer in women with DCIS, providing both preventive and therapeutic benefit [9, 10]. Oral TAM also has proven risk reduction value for women at increased risk for breast cancer, numbering over a million women in the United States alone [11, 12]. However, tamoxifen acceptance by DCIS and high-risk patients has been lower than expected, mainly because of toxicity concerns [13-16]. Serious adverse effects of TAM are related to its estrogen agonist activity on the endometrium, leading to an increased risk of endometrial cancer in postmenopausal women; and the activation of coagulation pathways leading to an increased risk of thromboembolism [11]. Hot flashes and vaginal symptoms were 20-30% more common in women aged 35-49 on tamoxifen than in the placebo group of the BCPT [17]. Together, these side effects are significant barriers to wide acceptance of TAM by DCIS patients [13] and high-risk women [18]. Although aromatase inhibitors are now proven to be efficacious for post-menopausal women [19, 20], these too have a burden of skeletal and possibly cardiovascular toxicity. There are no endocrine agents close to Phase 3 testing for pre-menopausal women. A particular challenge for primary and secondary breast cancer prevention efforts, therefore, is to devise an efficacious and non-toxic intervention which is likely to be widely accepted by women with DCIS and those at high risk for developing breast cancer. A potential solution is the development of delivery methods that preserve efficacy through targeted local delivery to the breast, but minimize toxicity because of low systemic exposure, as discussed in Sections 2.2 and 2.3.

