## 7. CLINICAL EVALUATIONS AND PROCEDURES

### 7.1 Schedule of Events

7.1.1 Expected duration of participation in the study: The interval from registration to the start of the intervention period will be a maximum of two weeks; the interval from Visit 1 (day of surgery) to Visit 2 is 1-21 days; and the (potential) interval from Visit 2 to the final phone call is up to 35 days. With an intervention period of 4 to 10 weeks, the minimum duration of participation is 29 days, and the maximum duration is 20 weeks.

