#### 11.1.2 AE Data Elements:

The following data elements are required for AE reporting.

- AE verbatim term
- NCI Common Terminology Criteria for Adverse Events version 4.0 (CTCAE v4.0) AE term (MedDRA lowest level term)
- CTCAE (MedDRA) System Organ Class (SOC)
- Event onset date and event ended date
- Treatment assignment code (TAC) at time of AE onset
- Severity grade
- Attribution to study agent (relatedness)
- Whether or not the event was reported as a SAE
- Whether or not the subject dropped due to the event
- Outcome of the event

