## 13.3 Accrual and Feasibility

13.3.1 Sample Size: We plan to accrue up to 108 subjects over 24 months. Therefore the monthly rate in the base period is 4.5. The distribution across institutions may be revised as the study progresses. The last participant will go off-treatment in month 27, and complete 30-day follow-up in month 28.

13.3.2 Gender distribution: will be entirely female. Although men do develop DCIS, the number is extremely small and it is unlikely that any men with DCIS will be seen at the recruiting sites over an 18 month period. Furthermore, the skin permeation characteristics of 4-OHT gel has never been studied in men, and may be different given different skin thickness in men and women. Finally, the target population for the study intervention is exclusively women; breast cancer prevention therapy for men is not a practical objective at this time.

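### From the day of surgery, non-serious AEs judged surgical need not be recorded, and the plan gives no single end to AE follow-up

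*Combined protocol and SAP*

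**What the plan says.** AE recording changes at surgery. Before it, 11.1.1.1 requires every AE after consent and baseline assessment, "through the day preceding the day of surgery must be recorded on the AE CRF (paper and/or electronic) whether or not related to study agent". From the day of surgery, 11.1.1.2 narrows this to "AEs not related to surgery that occur from the day of surgery through Study visit 2 (up to 21 days post surgery". It does not say who decides relation to surgery, or how.

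Serious events have their own rule in 11.1.1.3: "All SAEs, including all hospitalizations, during the study period will be reported as per DCP SAE reporting procedures". The single exception is "Hospitalization for planned surgery will not be reported", and a prolonged surgical stay becomes reportable again, with the AEs behind it entered on the AE CRF. The data elements in 11.1.2 hold one causality item, "Attribution to study agent (relatedness").

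On timing, 3.4 ends treatment the day before surgery, and 7.1.1 says "the interval from Visit 1 (day of surgery) to Visit 2 is 1-21 days". The only scheduled contact after Visit 2 is a call to premenopausal women who have had no period since surgery (7.5). Its script in Appendix D asks only about menses. Section 13.3.1 states: "The last participant will go off-treatment in month 27, and complete 30-day follow-up in month 28". Section 3.10 has the last participant finished by month 27.

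**The concern.** The relatedness filter begins just when observation off drug begins, and some events then have two plausible causes. Section 2.1 names "the activation of coagulation pathways leading to an increased risk of thromboembolism" as a serious effect of tamoxifen, and surgery is another plausible cause of a postoperative thrombosis. Skin reactions to the gel are part of secondary objective 6, and the operation is on a gel-treated breast. If such an event is non-serious and is put down to surgery, 11.1.1.2 does not require it on the AE CRF. With no field for surgical relatedness, nobody can later count what was left out or repeat the analysis with it included.

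Section 13.5.4 compares the proportion of women with each AE type, at any grade, by Fisher's exact test. Non-serious events make up part of those counts, so at stake is how complete a small safety comparison is. The unclear end of follow-up adds to this, because observation after the last dose differs from woman to woman and sections of the plan disagree on when it stops.

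**Working it through.** **Step 1. Reproduce the plan's own durations.** Minimum participation in 7.1.1: 4 weeks × 7 + 1 day = 29 days, as stated. Maximum: 2 weeks to start + 10 weeks of treatment + 3 weeks to Visit 2 + 5 weeks to the final call = 20 weeks, as stated. Section 13.3.1: month 27 + 30 / (365.25/12) = 27.99, which matches month 28. Each figure is sound by itself.

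**Step 2. Trace each kind of event through the rules.**

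| Event | Governing text | Required? |
|---|---|---|
| Any AE with onset before surgery, including a gel skin reaction | 11.1.1.1 | Yes, no filter |
| Serious event from surgery on (admission or prolonged stay, life-threatening, important medical event) | 11.1.1.3, 11.2.1 | Yes, reported as an SAE whatever its relation to surgery |
| Non-serious, surgery to Visit 2, judged unrelated to surgery | 11.1.1.2 | Yes |
| Non-serious, surgery to Visit 2, judged related to surgery | 11.1.1.2 | No, unless it lies behind a prolonged stay |
| Non-serious, after Visit 2 | None | No |
| Serious, after Visit 2 | 11.1.1.3 | Unclear: the end of the study period is not defined |

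The fourth row is the gap. It includes a thromboembolic event managed without admission and not classed as an important medical event, and a new skin or wound event on the treated breast.

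**Step 3. Measure the window.** Let v be the day of Visit 2 after surgery, from 1 to 21. With the last dose on the day before surgery, days from last dose to Visit 2 = v + 1.

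| Visit 2 | From surgery | Short of 30 | From last dose | Short of 30 |
|---|---|---|---|---|
| Day 1 | 1 | 29 | 2 | 28 |
| Day 21 | 21 | 9 | 22 | 8 |

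No permitted Visit 2 reaches 30 days by either count, and the permitted dates span 21 − 1 = 20 days. Section 8.3 provides for women who stop early. A woman who stopped 6 days before surgery has v + 6 days, that is 7 to 27, and one who stopped 9 days before could reach 9 + 21 = 30. The last-dose figures therefore apply only to women dosed to the day before surgery.

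**Step 4. Compare the stated ends.** AE recording closes at Visit 2, at most day 21 (11.1.1.2). Participation ends by month 27 (3.10). A 30-day follow-up ends in month 28 (13.3.1). The final call is up to 35 days after Visit 2 (3.7, 7.5), which can be 21 + 35 = 56 days after surgery, yet Appendix D labels the same call as up to 35 days after surgery.

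**Step 5. Scale.** At most 100 women start treatment. Assuming the 1:1 split holds among them, that is 50 per arm, and each omitted woman shifts an AE proportion by 1/50 = 2 percentage points. The documents give no rate for such events, so the number lost cannot be estimated.

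**The case against.** Leaving expected surgical AEs off the form is an understandable choice in a pre-surgical trial. Recording every wound event would add surgical noise to the any-grade comparisons. Much of the safety picture is also protected elsewhere:

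- Serious events and hospitalizations are reported whatever their relation to surgery, and 11.2.1 allows an event to be serious without admission.
- Gel reactions that begin during treatment are recorded unfiltered. AEs are checked at the week 1, 4 and 8 calls as surgery timing allows, and at surgery or the day before.
- Visit 2 is meant to document resolution of study-related symptoms.
- The prespecified toxicity endpoints are coagulation proteins, estrogenic markers, BESS symptoms and skin reactions. None of them is a count of clinical thromboembolic events.

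All of this stands, and it rules out some stronger readings. A reader might infer that thromboembolism in general goes unrecorded; 11.1.1.3 contradicts that. A reader might infer bias between arms; the trial is double-blind and the filter and Visit 2 timing apply alike to both, so what is shown is under-ascertainment. A reader might take 30 days as a required AE window that the schedule fails to deliver to every participant. But 13.3.1 is a timeline sentence under accrual and names no AE assessment, and early stopping breaks any claim about every woman. Visit 2 on day 1 is permitted, but it is unlikely to be common, because 3.7 expects the final pathology report to be out by then.

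None of this closes the fourth row of the table in Step 2, supplies criteria or a field for surgical relatedness, or reconciles the different end dates.

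**Conclusion.** The point holds for non-serious events. From surgery to Visit 2 they need be recorded only if judged unrelated to surgery, with no criteria and no trace of the exclusion. Non-serious thromboembolic events and new skin or wound events on the treated breast can therefore be missing from the 13.5.4 comparison in both arms. The cost is sensitivity and lost detail among at most 100 treated women. The number of events cannot be given from the documents.

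The second part is an internal inconsistency. AE recording ends 1 to 21 days after surgery, or 2 to 22 days after a last dose taken the day before surgery. Section 13.3.1 speaks of 30 days and month 28, 3.10 of month 27, and no scheduled contact delivers a 30-day follow-up. The documents do not establish that 30 days is the correct AE window, only that these sections disagree.

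This rests on reading 11.1.1.2 as written and on the 11.1.2 list being the required AE data elements. Whether a serious event attributed to surgery is also entered on the AE CRF, beyond the prolonged-stay case, is not spelled out; the conclusion does not depend on it.

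**What to change.** 1. In 11.1.1.2, require thromboembolic events and skin or wound events on the treated breast to be recorded from the day of surgery whatever their relation to surgery. Other expected surgical AEs can stay excluded.
2. In 11.1.2, add a field for relation to surgery beside agent attribution, and say in 13.5.4 that these AE types will be shown with and without surgery-attributed events.
3. State one end of AE and SAE follow-up, the same for all participants, and reconcile 3.7, 3.10, 7.1.1, 7.5, 11.1.1, 13.3.1 and Appendix D to it. Define the end of the study period used in 11.1.1.3 at the same time.

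The first two items cost protocol and CRF wording, one form field, and some extra AE entries for expected surgical events. The third costs wording only, unless the chosen end falls after Visit 2; each participant then needs one short call or email. Recording all surgical AEs would be a larger trade-off and is not needed to close this gap.

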#### 11.1.2 AE Data Elements:

The following data elements are required for AE reporting.

- AE verbatim term
- NCI Common Terminology Criteria for Adverse Events version 4.0 (CTCAE v4.0) AE term (MedDRA lowest level term)
- CTCAE (MedDRA) System Organ Class (SOC)
- Event onset date and event ended date
- Treatment assignment code (TAC) at time of AE onset
- Severity grade
- Attribution to study agent (relatedness)
- Whether or not the event was reported as a SAE
- Whether or not the subject dropped due to the event
- Outcome of the event

#### 11.1.3 Severity of AEs

11.1.3.1 Identify the AE using the CTCAE version 4.0. The CTCAE provides descriptive terminology (MedDRA lowest level term) and a grading scale for each AE listed. A copy of the CTCAE can be found at [http://ctep.cancer.gov/protocolDevelopment/electronic\\_applications/ctc.htm](http://ctep.cancer.gov/protocolDevelopment/electronic_applications/ctc.htm).

AEs will be assessed according to the grade associated with the CTCAE term. AEs that do not have a corresponding CTCAE term will be assessed according to the general guidelines for grading used in the CTCAE v4.0. as stated below.

#### **CTCAE v4.0 general severity guidelines:**

Grade	Severity	Description
1	Mild	Mild; asymptomatic or mild symptoms; clinical or diagnostic observations only; intervention not indicated.
2	Moderate	Moderate; minimal, local or noninvasive intervention indicated; limiting age-appropriate instrumental activities of daily living (ADL)*.
3	Severe	Severe or medically significant but not immediately life-threatening; hospitalization or prolongation of hospitalization indicated; disabling; limiting self-care ADL**.
4	Life-threatening	Life-threatening consequences; urgent intervention indicated.

Grade	Severity	Description
5	Fatal	Death related to AE.

## ADL

\*Instrumental ADL refers to preparing meals, shopping for groceries or clothes, using the telephone, managing money, *etc.*

\*\*Self-care ADL refers to bathing, dressing and undressing, feeding self, using the toilet, taking medications, and not bedridden.

### 11.1.4 Assessment of relationship of AE to treatment

The possibility that the AE is related to study agent will be classified as one of the following: not related, unlikely, possible, probable, definite.

### 11.1.5 Follow-up of AEs

All AEs, including lab abnormalities that in the opinion of the investigator are clinically significant, will be followed according to good medical practices and documented as such.

## 11.2 Serious Adverse Events

11.2.1 DEFINITION: Regulations at 21 CFR §312.32 (revised April 1, 2014) defines an SAE as any untoward medical occurrence that at any dose has one or more of the following outcomes:

- Death
- A life-threatening AE
- Inpatient hospitalization or prolongation of existing hospitalization
- A persistent or significant incapacity or substantial disruption of the ability to perform normal life functions
- A congenital anomaly or birth defect
- Important medical events that may not be immediately life-threatening or result in death or hospitalization should also be considered serious when, based upon appropriate medical judgment, they may jeopardize the patient *and* may require intervention to prevent one of the other outcomes.

### 11.2.2 Reporting SAEs to DCP

11.2.2.1 The Lead Organization and all Participating Organizations will report SAEs on the DCP SAE Report Form found at <http://prevention.cancer.gov/clinical-trials/clinical-trials-management/protocol-information-office/pio-instructions-and-tools/2012-consortia>.

11.2.2.2 Contact the DCP Medical Monitor by phone within 24 hours of knowledge of the event.

Name: [name]  
Address: Division of Cancer Prevention  
National Cancer Institute  
[name]  
[name]  
[contact] (during normal business hours)

[contact]  
Email: [contact]

Include the following information when calling the Medical Monitor:

- Date and time of the SAE
- Date and time of the SAE report
- Name of reporter
- Call back phone number
- Affiliation/Institution conducting the study
- DCP protocol number
- Title of protocol
- Description of the SAE, including attribution to drug

11.2.2.3 The Lead Organization and all Participating Organizations will email written SAE reports to the following recipients within 48 hours of learning of the event using the fillable PDF SAE Report Form

- DCP's Regulatory Contractor, CCS Associates, email ([[contact]](mailto:[contact]))
- Lead Organization (Northwestern University), email ([[contact]](mailto:[contact]))
- BHR Pharma, LLC, email ([[contact]](mailto:[contact]))
- Besins Pharmacovigilance, email ([[contact]](mailto:[contact]))

11.2.2.4 The DCP Medical Monitor and CCSA regulatory and safety staff will make an initial assessment of the SAE and communicate with BHR Pharma, LLC who will determine which SAEs require FDA submission as IND safety reports.

11.2.2.5 BHR Pharma, LLC will provide a standard report for the Lead Organization and all Participating Organizations to comply with applicable regulatory requirements related to reporting SAEs to the CIRB/IRB/IEC.

### 11.2.3 Follow-up of SAE

Site staff should send follow-up reports as requested when additional information is available. Additional information should be entered on the DCP SAE Report Form in the appropriate format. Follow-up information should be sent to DCP as soon as available, with a copy to the Lead Organization ([[contact]](mailto:[contact])) and BHR Pharma, LLC ([[contact]](mailto:[contact])).

## 12. STUDY MONITORING

### 12.1 Data Management

Data will be managed by the study statistician, [name], according to standard operating procedures, which meet the guidelines of DCP Requirements for Data Management and which follow the Data Management Plan that Northwestern University has on file with the Division of Cancer Prevention, NCI. The Consortia 2012 Data Management Plan, submitted as part of a contract agreement with the NCI (HHSN261201200035I), was approved.

### 12.2 Case Report Forms

Participant data will be collected using protocol-specific case report forms (CRFs) developed from the standard set of DCP Chemoprevention CRF Templates and utilizing NCI-approved Common Data

Elements (CDEs). The approved CRFs will be used by Northwestern University to create the electronic CRF (e-CRF) screens in the Robert H. Lurie Comprehensive Cancer Center of Northwestern University (Lurie Cancer Center) Clinical Trials Management System (CTMS). Accrual-site staff will enter data into the e-CRFs for transmission to DCP according to DCP standards and procedures.

### **12.3 Source Documents**

All source documents will be collected and stored in the Clinical Research Office of the site where the participant was accrued. Any data recorded directly on CRFs that constitute no prior written or electronic record of data, will be specifically identified as source data. BESS questionnaires completed in person may be completed directly on the paper CRF and need not be transcribed from separate source documentation.

### **12.4 Data and Safety Monitoring Plan**

A comprehensive Data Safety and Monitoring Plan has been submitted by Northwestern University, approved by the DCP, and is on file there. Any future changes will be forwarded for review.

### **12.5 Sponsor or FDA Monitoring**

The NCI, DCP (or their designee), pharmaceutical collaborator (or their designee), or FDA may monitor/audit various aspects of the study. These monitors will be given access to facilities, databases, supplies and records to review and verify data pertinent to the study.

### **12.6 Record Retention**

Clinical records for all participants, including CRFs, all source documentation (containing evidence to study eligibility, history and physical findings, laboratory data, results of consultations, *etc.*), as well as IRB records and other regulatory documentation will be retained by the Investigator in a secure storage facility in compliance with Health Insurance Portability and Accountability Act (HIPAA), Office of Human Research Protections (OHRP), Food and Drug Administration (FDA) regulations and guidances, and NCI/DCP requirements, unless the standard at the site is more stringent. The records for all studies performed under an IND will be maintained, at a minimum, for two years after the approval of a New Drug Application (NDA). For NCI/DCP, records will be retained for at least three years after the completion of the research. NCI will be notified prior to the planned destruction of any materials. The records should be accessible for inspection and copying by authorized persons of the Food and Drug Administration. If the study is done outside of the United States, applicable regulatory requirements for the specific country participating in the study also apply.

### **12.7 Cooperative Research and Development Agreement (CRADA)/Clinical Trials Agreement (CTA)**

The agent(s) supplied by DCP, NCI, used in this protocol, is/are provided to the NCI under a Collaborative Agreement (CRADA, CTA) between the Pharmaceutical Company(ies) (hereinafter referred to as Collaborator(s)) and the NCI Division of Cancer Prevention. Therefore, the following obligations/guidelines, in addition to the provisions in the "Intellectual Property Option to Collaborator@ contained within the terms of award, apply to the use of Agent(s) in this study:

12.7.1 Agent(s) may not be used for any purpose outside the scope of this protocol, nor can Agent(s) be transferred or licensed to any party not participating in the clinical study. Collaborator(s) data for

Agent(s) are confidential and proprietary to Collaborator(s) and shall be maintained as such by the investigators. The protocol documents for studies utilizing investigational agents contain confidential information and should not be shared or distributed without the permission of the NCI. If a patient participating on the study or participant's family member requests a copy of this protocol, the individual should sign a confidentiality agreement. A suitable model agreement can be downloaded from the DCP website.

12.7.2 For a clinical protocol where there is an Investigational Agent used in combination with (an) other investigational Agent(s), each the subject of different collaborative agreements, the access to and use of data by each Collaborator shall be as follows (data pertaining to such combination use shall hereinafter be referred to as "Multi-party Data").

12.7.3 NCI must provide all Collaborators with prior written notice regarding the existence and nature of any agreements governing their collaboration with NIH, the design of the proposed combination protocol, and the existence of any obligations that would tend to restrict NCI's participation in the proposed combination protocol.

12.7.4 Each Collaborator shall agree to permit use of the Multi-Party Data from the clinical trial by any other Collaborator solely to the extent necessary to allow said other Collaborator to develop, obtain regulatory approval, or commercialize its own investigational agent.

12.7.5 Any Collaborator having the right to use the Multi-Party Data from these trials must agree in writing prior to the commencement of the trials that it will use the Multi-Party Data solely for development, regulatory approval, and commercialization of its own investigational agent.

12.7.6 Clinical Trial Data and Results and Raw Data developed under a collaborative agreement will be made available exclusively to Collaborator(s), the NCI, and the FDA, as appropriate. All data made available will comply with HIPAA regulations.

12.7.7 When a Collaborator wishes to initiate a data request, the request should first be sent to the NCI, who will then notify the appropriate investigators of Collaborator's wish to contact them.

12.7.8 Any manuscripts reporting the results of this clinical trial must be provided to DCP for immediate delivery to Collaborator(s) for advisory review and comment prior to submission for publication. Collaborator(s) will have 30 days (or as specified in the CTA) from the date of receipt for review. Collaborator shall have the right to request that publication be delayed for up to an additional 30 days in order to ensure that Collaborator's confidential and proprietary data, in addition to Collaborator(s)'s intellectual property rights, are protected. Copies of abstracts must be provided to DCP for forwarding to Collaborator(s) for courtesy review as soon as possible and preferably at least three days prior to submission, but in any case, prior to presentation at the meeting or publication in the proceedings. Press releases and other media presentations must also be forwarded to DCP prior to release. Copies of any manuscript, abstract, and/or press release/ media presentation should be sent to the Protocol Information Office at [NCI\\_DCP [contact]](mailto:NCI_DCP [contact]).

The Protocol Information Office will forward manuscripts to the DCP Project Officer for distribution to the Collaborator(s). No publication, manuscript or other form of public disclosure shall contain any of Collaborator's confidential/proprietary information.

